7.6.4 Progression-free survival by Subsets

Subset analyses performed for overall survival will also be performed for PFS (**Table 37**).

7.6.5 Treatment Response

All patients will have their best response on study classified every 8 weeks until disease progression, using the RECIST (Response Evaluation Criteria in Solid Tumors) criteria 1.1. The best response to protocol treatment is determined by investigators for patients who permanently discontinued protocol treatment and collected in “Best Objective Response RECIST 1.1” section of END OF TREATMENT REPORT. For patients who are still on protocol treatment and followed for response at final clinical cut-off, their best response is defined as the “best verified” response they have achieved up to the time of clinical cut-off determined by CCTG Senior Investigator based on data on “Response Assessment” section of TREATMENT REPORT or BEST SUPPORTIVE CARE REPORT.

Best response to protocol treatment will be summarized for all randomized patients (**Table 38**).

The primary analysis of response will be the comparison of the objective response rate (CR+PR) between treatment arms among all the randomized patients using the Cochran-Mantel-Haenszel (CMH) statistic adjusted for stratification factor for all randomized patients (**Table 39**) as defined in Section 6.

In addition, a stratified logistic regression model adjusted for covariates will be applied to verify the impact of the prognostic factors on the treatment effect (**Table 39**). For all stratified logistic regression models, estimates of the odds ratio(s) and 90% confidence interval(s) will be given.

Stratified logistic regression odds ratios will be estimated using PROC PHREG in SAS [5]. A dummy time variable will be created, where all responders will be classified as events with an arbitrary time = t_0 , and non-responders as censored with time t_1 , where $t_1 > t_0$. The DISCRETE option will be used for tied observations.

Coding for treatment, stratification variable and prognostic factors is identical to that presented in Section 7.4.1.

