5.2 Patient Evaluation Flowsheet: Pre-Treatment, On-Study, and after Protocol Treatment
 For Patients Randomized to Durvalumab and Tremelimumab (Arm 2)

| Required Investigations | PRE-STUDY (≤14 days prior to randomization, unless otherwise indicated) | DURING Protocol Treatment Day 1 each cycle, and as clinically indicated (unless otherwise indicated) | AFTER Protocol Treatment is Permanently Discontinued ¹ | | | |
|---|--|---|---|--------------------------|---|---------------------------|
| | | | PRIOR to objective disease progression | | AFTER objective disease progression | |
| | | | 4 weeks after end of last cycle date | Every 4 weeks thereafter | 4 weeks after end of last cycle date ¹ | Every 12 weeks thereafter |
| History and Physical Exam² | | | | | | |
| Including: height (baseline only), weight, ECOG performance status, clinical tumour measurements (if applicable) | X | X | X | X | X | |
| Vital Signs (blood pressure, heart rate, temperature) | X | X ³ | | | | |
| Concomitant Medications | X | X | X | | X | |
| Overall Survival | | | | | | |
| Survival status assessment | | X | X | X | X | X ⁴ |
| Hematology^{2,5} | | | | | | |
| CBC, differential (including lymphocytes), platelets | X | X ² | X | X | X | X ⁵ |
| Coagulation^{2,5} | | | | | | |
| PTT, PT/INR | X | X ² | X | X | X | X ⁵ |
| Biochemistry^{2,5} | | | | | | |
| Serum Creatinine, Chloride, Sodium, Potassium, Calcium, Magnesium, Bilirubin, ALP, AST and ALT, LDH, Albumin, TSH ⁶ , Amylase, Lipase, Serum CEA | X | X ² | X | X | X | X ⁵ |
| Creatinine Clearance (calculated) | X | as clinically indicated | | | | |
| Glucose | X | as clinically indicated | | | | |
| Radiology⁷ | | | | | | |
| Chest/abdomen/pelvis CT or MRI scan | X ≤ 28 days | X ⁷ Every 8 weeks from randomization until objective disease progression (maintain schedule even if cycles are delayed) | | | | |
| Other scans as necessary to document all measurable and non-measurable disease | X ≤ 28 days | | | | | |
| Other Investigations | | | | | | |
| Pregnancy Test ⁸ | X | | | | | |
| ECG | X | as clinically indicated | | | | |
| Dipstick Urinalysis (including protein, specific gravity, glucose and blood) | X | | | | | |

table continued on next page ...

ADMIN UPDATE #1: 2018-JAN-24

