| 
 All patients will be seen at 4 weeks after the end of the last cycle date. Thereafter, continued follow-up is not required for patients who go off protocol treatment with unequivocal progressive disease, except to document ongoing toxicities (until resolved to < grade 2) and late toxicities (including second malignancies). For patients who go off protocol treatment with CR, PR, or SD ongoing, follow-up will be required every 12 weeks until relapse (see Appendix I for investigations to be performed). Death Report will be required for all patients. Due within 2 weeks of knowledge of death (see Appendix IV - Documentation for Study). Timing of Day 1 Assessments: Pre-treatment blood draws and physical exams may be done one working day prior to treatment if necessary, and when treatment is to begin on a Monday, may be done on the previous Friday (maximum 72 hours prior to treatment). In order to ensure that nadir counts are not missed, every effort should be made to do interim blood draws within 24 hours of the day specified in the protocol. If a patient shows an AST or ALT ≥ 3 x ULN together with total bilirubin ≥ 2 x ULN, refer to Appendix III for further instructions on cases of increases in liver biochemistry and evaluation of Hy's Law. These cases should be reported as SAEs if, after evaluation, they meet the criteria for a Hy's law case or if any of the individual liver test parameters fulfill any of the SAE criteria. Note: Labs do not need to be repeated Day 1, Cycle 1. In order to ensure that nadir counts are not missed, every effort should be made to do interim blood draws within 24 hours prior to the day specified in the protocol. Vital signs are to be monitored before, during, and after the infusion of tremelimumab and durvalumab with assessment of vital signs to be collected ≤ 30 minutes prior to start of infusion then every 30 ± 5 minutes during infusion and observation periods. A 1-hour observation period is recommended after the first infusion of tremelimumab, during which time durvalumab may be administered (see Section 7.1.3). A second 1-hour observation period is recommended after the first infusion of durvalumab. If no clinically significant infusion reactions are observed during or after the first cycle of tremelimumab and durvalumab, subsequent infusion observation periods can be at the Investigator's discretion but are recommended to be of 30 minutes, i.e., 30 minutes after tremelimumab infusion, during durvalumab infusion, and for 30 minutes after durvalumab infusion. For patients who receive only durvalumab, the recommended observation period is 30 minutes after infusion. In the event that patient is unable to attend clinic, post-progression follow-up may be by means of telephone contact. Hematology, Coagulation and Biochemistry investigation to be done after objective progression ONLY if there are ongoing hematologic AEs that are related to protocol treatment. If abnormal, T3 and T4 must be measured. To ensure comparability, scans must identify and report each lesion at baseline and at reassessment during treatment. These scans must be performed using identical technique (i.e. scans performed immediately following bolus contrast administration using a standard volume of contrast, the identical contrast agent, and preferably the same scanner). Tumour evaluations must be consistently performed every 8 weeks (i.e. at 8 weeks, 16 weeks, 24 weeks, 32 weeks etc. from randomization) until objective disease progression is documented (as described in Section 8). Sites should adhere to this calendar-based schedule regardless of any delays in treatment. If a radiology scan is done off schedule, future protocol-required scans should still be performed based on the original schedule, i.e. every 8 weeks counting from randomization (not from the date of the off schedule scan). For women of childbearing potential only. May be urine or serum. Pregnancy test (in women of childbearing potential), as part of Pre-Study Evaluation, may include an ultrasound to rule-out pregnancy. See Section 12.0 and the CO.26 Correlative Studies Laboratory Manual for details. Whole blood, plasma and serum should be obtained as close to the time of objective progression as possible and should be done within 28 days (e.g. at the next clinic visit). Blood for correlatives done within 28 days PRIOR to date of progression does not need to be repeated. Adverse Events to be evaluated using the NCI Common Terminology Criteria for Adverse Events (CTCAE v4.0) (see Appendix V). See Section 7 and Appendix III for additional monitoring of patients with toxicity. Follow every adverse event felt related to study therapy until resolved to ≤ grade 2 – i.e. follow-up every 12 weeks until deterioration to ECOG PS 4 and/or end of life care or until all toxicities thought to be possibly-, probably-, or definitely-related to durvalumab or tremelimumab have resolved, returned to baseline, or been deemed irreversible, whichever is longer. To be completed by patient in clinic. | | | | | | |

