| Treatment Report (Arm 2 only) | Every 4 weeks (28 days) while patient is on protocol treatment | Within 2 weeks of the end of each 4 week reporting period | If available/applicable: 
 • CT/MRI abdomen/pelvis report • CT/MRI chest • other radiology reports • tumour measurement worksheet • ECG report |

table continues on next page ...

| Electronic Folder | Timing | To be completed electronically | Supporting Documentation Required ¹ |
|--|---|---|--|
| End of Treatment Report(Arm 2 only) | As soon as permanent off treatment status is confirmed. | Within 2 weeks of end of treatment | |
| 4-Week Post-Treatment Follow-Up Report (Arm 2 only) | 4 weeks from the date of last infusion | Within 2 weeks of the 4-week post treatment follow up visit | 
 • relevant radiology reports |
| Follow-up Report ³ (Arm 2 only) | Every 4 weeks (28 days) until objective progression | Within 2 weeks of follow-up visit | If available/applicable: 
 • CT/MRI abdomen/pelvis report • tumour measurement worksheet • CT/MRI chest report • other radiology reports • ECG report |
| Short Follow-up Report | Every 12 weeks after objective disease progression | Within 2 weeks of follow-up visit | |
| Relapse/Progression Report | Upon the patient's objective disease progression / relapse | Within 4 weeks of confirmation | 
 • relevant radiology, operative and pathology reports |
| Death Report | Upon patient's death | Within 4 weeks of patient death | 
 • autopsy/post-mortem report, if performed |
| Serious Adverse Event (SAE) Report ⁴ | Within 24 hours of event At time of event and reported to CCTG | Within 1 working day ⁴ | |
| Minimal Follow-up Report ⁵ | Annual | Within 6 weeks of contact | If available/applicable: 
 • autopsy report • CT/MRI report |

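### SAP 7.6.5 takes best response after stopping treatment only from an Arm 2 form due within 2 weeks, so an Arm 2 response first documented later, before progression, may go uncounted

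*SAP*

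**What the plan says.** SAP 7.6.5 opens with one window for everyone: "All patients will have their best response on study classified every 8 weeks until disease progression". Two source rules follow.

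- **Off treatment.** "The best response to protocol treatment is determined by investigators for patients who permanently discontinued protocol treatment and collected in" the RECIST 1.1 best-response section of the End of Treatment Report.
- **Still on treatment at cut-off.** This rule opens with "For patients who are still on protocol treatment and followed for response at final clinical cut-off, their best response is defined as". It relies on whichever verified response was highest so far, as judged by the CCTG Senior Investigator from the Treatment Report or the Best Supportive Care Report.

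Protocol Appendix IV sets the forms.

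- The End of Treatment Report is Arm 2 only, to be completed "Within 2 weeks of end of treatment".
- The Follow-up Report, also Arm 2 only, runs "Every 4 weeks (28 days) until objective progression" and lists CT/MRI reports and the tumour measurement worksheet as supporting documents.
- The 4-Week Post-Treatment Follow-Up Report, Arm 2 only, lists radiology reports.
- The Best Supportive Care Report, Arm 1 only, has the same 4-weekly timing to objective progression.

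The protocol 5.2 flowsheet requires Arm 2 imaging "Every 8 weeks from randomization until objective disease progression (maintain schedule even if cycles are delayed". Section 10.1 asks sites to keep to the investigation schedule after treatment stops. Section 13.2 defines ORR as documented CR or PR by RECIST 1.1 in all randomized patients and sets no on-treatment limit.

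**The concern.** ORR is a secondary between-arm comparison in all randomized patients, so responses should be looked for over the same period in both arms. As written, the source rule for Arm 2 patients off treatment is a form completed around the time they stop. The natural BSC source is a form that continues to progression. The rule can therefore be narrower than the opening sentence of 7.6.5 and narrower than the protocol's ORR definition, and it can be so in Arm 2 only.

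The patients concerned are foreseen. Section 10.1 allows stopping for toxicity, intercurrent illness or patient request. Footnote 1 to the 5.2 flowsheet provides for patients who stop with CR, PR or SD ongoing. SAP Table 35 has a row for progression off study treatment. Nor is the SAP unaware of the later forms: it uses the 4-Week Post-Treatment and Follow-up Reports for the last date known alive (7.6.1) and for anti-cancer treatment before progression (7.8), but not for response.

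If a response is missed in this way, the Arm 2 ORR is too low. The error would run against the experimental arm.

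**Working it through.** **1. The plan's own figure.** The documents give no power or target for ORR, so there is no ORR figure to reproduce. The only design figure is 150 deaths for OS. Schoenfeld's formula with 2:1 allocation, two-sided alpha 10%, power 80% and HR 0.65 gives (1.645 + 0.842)² / [(2/3)(1/3)(ln 0.65)²] = 6.18 / 0.0412 ≈ 150. It reproduces, and this point does not affect it.

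**2. The passages side by side.**

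| Question | Arm 2, stopped without progression | BSC |
|---|---|---|
| Imaging | 8-weekly to objective progression (5.2) | 8-weekly to objective progression (5.1) |
| Forms covering that period | 4-Week Post-Treatment and Follow-up Reports | Best Supportive Care Report |
| Response source in SAP 7.6.5 | End of Treatment Report only | Best Supportive Care Report |

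Read literally, 7.6.5 names the Best Supportive Care Report only for patients still followed at cut-off. BSC patients who progressed or died earlier have no named source, but that report is plainly the one intended.

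**3. Who can be affected.** Only an Arm 2 patient who stops before objective progression and whose first CR or PR is documented after the End of Treatment entry but before progression. A patient who stops at RECIST 1.1 progression loses nothing.

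**4. Timing of the form against the next scan.** Scans fall every 56 days from randomization and the form is due 14 days after stopping. If stopping days are spread evenly over the scan interval (an assumption), the share whose next scheduled scan falls after the due date is (56 − 14)/56 = 42/56 = 75%. If patients stop at an on-schedule Day 1 visit (weeks 4, 8, 12, 16 and so on), the next scan is 4 or 8 weeks away, always beyond the due date. This shows that the form is usually due before the next scan. It does not show that the entry is closed by then.

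**5. Size per missed response.** The SAP plans 120 patients in Arm 2 (section 2.1).

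- 1 missed: 1/120 = 0.83 points
- 2 missed: 2/120 = 1.67 points
- 3 missed: 3/120 = 2.50 points

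**6. Illustrative range.** The documents give no rates, so these are assumptions. Let s be the share of Arm 2 stopping without progression and r the share of those who first respond later. Expected missed responses are 120 × s × r, and the loss in ORR is 100 × s × r points.

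- s = 5%, r = 2%: 120 × 0.05 × 0.02 = 0.12 responses, 0.1 points
- s = 20%, r = 10%: 120 × 0.20 × 0.10 = 2.4 responses, 2.0 points

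**The case against.** The strongest reply is that a due date is not a data lock. Nothing says the best-response field closes at 2 weeks, and completion conventions sit in a data management guidebook that is not part of these documents. A reader might infer that the Arm 2 response window definitely ends at the End of Treatment Report. The documents do not support that. What stands is that they do not require an update either, so the counted response depends on unstated site practice.

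Second, few patients can be affected. Sections 7.1.7, 8.2 and 10.2 encourage treatment to continue until progression is unequivocal, so for many patients the form will come at or after RECIST progression. That is accepted and limits the size.

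Third, 7.6.5 speaks of response to protocol treatment, and therapy after stopping is at the investigator's discretion, so counting every later scan could credit another drug. This is a fair point, and the fix needs a rule for it.

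Other stronger readings also go too far.

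- The remark in protocol section 2.0 about late responses to anti-CTLA-4 agents describes slow response and pseudoprogression. It is not evidence of first responses after stopping without progression.
- SAP 7.6.7 might be read as using a wider responder set than 7.6.5, but its wording also fits the same set.
- The missing literal source for BSC patients who progressed before cut-off is a wording gap, not evidence that BSC responses would be lost.
- Without response or discontinuation rates, nothing can be said about whether the ORR test result would change.

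**Conclusion.** The point holds in a limited form. The stated source rule for Arm 2 patients off treatment can be narrower than the SAP's own response window and the protocol's ORR definition, and no equivalent restriction applies to BSC. Whether any response is lost depends on whether the End of Treatment entry is updated after later scans, which the documents do not say. The number affected is unknown and probably small. Each missed response costs 0.83 points of Arm 2 ORR, and the assumed ranges above give 0.1 to 2.0 points. OS and PFS are unaffected.

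Two further limits apply. That the follow-up forms hold response information is inferred from the radiology reports and worksheets listed with them. Also, follow-up after stopping without progression is described inconsistently. Footnote 1 to the 5.2 flowsheet says "For patients who go off protocol treatment with CR, PR, or SD ongoing, follow-up will be required every 12 weeks until relapse", while the flowsheet itself has 4-weekly visits and 8-weekly scans and Appendix IV has a 4-weekly report. These passages must be reconciled, but under either description follow-up continues after the End of Treatment Report is due.

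This is a cheap improvement to a secondary endpoint, not a threat to the trial's main conclusion.

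**What to change.** Amend SAP 7.6.5 as follows.

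1. Derive best response in both arms from all RECIST 1.1 assessments from randomization to first objective progression, death or clinical cut-off, whichever comes first.
2. Name the sources: the Treatment, 4-Week Post-Treatment and Follow-up Reports, with their radiology reports and any tumour worksheets, for Arm 2; the Best Supportive Care Report for every BSC patient, including those who progressed or died before cut-off.
3. Keep the investigator's End of Treatment entry, and reconcile it against later assessments.
4. In both arms, count only assessments before the start of any new anti-cancer therapy in the main ORR. Add a sensitivity analysis that includes later ones. SAP 7.6.3 already relies on the start date of such therapy.
5. State that 7.6.7 uses the same responder set.

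Separately, reconcile the 12-weekly wording in footnote 1 to protocol 5.2 with the flowsheet and Appendix IV.

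The cost is some SAP wording and a little more derivation work, with no new scans or forms. The downside is that ORR is no longer simply the investigator's end-of-treatment entry, so differences between that entry and the derived response will have to be resolved and documented.

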13.3 Sample Size and Duration of Study

The study is designed to have a power of 80% and a two-sided alpha of 10% to detect a 35% reduction in the continuous risk of death (HR 0.65, which corresponds to an increase of median survival from 4.5 to 6.9 months). It is estimated that 150 events will be required to detect this reduction. The final analysis will be performed when 150 events are observed. Assuming an accrual rate of around 10 patients per month, the required number of events would be observed by accruing a total of 180 patients and following them for a minimum of 6 months. The total duration of the trial would be around 24 months.

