2.1 Study Design

Study CCTG CO.26 is a multi-centre, open-label, randomized phase II trial of durvalumab and tremelimumab combined with best supportive care *versus* best supportive care alone (where best supportive care is defined as those measures

designed to provide palliation of symptoms and improve quality of life as much as possible) in patients with refractory, advanced colorectal carcinoma. Patients are stratified by ECOG performance status (0 vs. 1) and site of tumour (right colon vs. transverse colon vs. left colon vs. rectum vs. unknown) prior to randomization. This study is conducted by CCTG with support from AstraZeneca. CCTG Case Report Forms (CRFs) are used and the database are maintained by CCTG.

A total of 180 patients would be enrolled (120 on Durva+Treme and 60 on BSC). The final analyses will be performed by CCTG when the required number of deaths (150) is recorded. This analysis plan describes the analyses performed at the completion of the study.

This study was activated on August 10, 2016 and closed to randomization of patients on June 29, 2017 after 180 patients were randomized. The CCTG Data Safety Monitoring Committee has been reviewing safety data every six months (usually at the time of the bi-annual CCTG Spring and Fall meetings) and as otherwise required. These analyses have been prepared by a CCTG/Queen's Senior Biostatistician.

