2.2 Treatment Allocation

The study is planned to randomize 180 subjects using a 2:1 allocation to durvalumab and tremelimumab combined with best supportive care (Durva+Treme Arm or ARM 2) and best supportive care alone (BSC Arm or ARM 1). The randomization was dynamically balanced by ECOG performance status (0 vs. 1) and site of tumour (right colon vs. transverse colon vs. left colon vs. rectum vs. unknown) using the method of minimization. A centralized system was used to randomize all patients in this study.

3. Objectives

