4.3 Safety

The safety endpoints are serious and non-serious adverse events (clinical and laboratory), laboratory parameters, dosing data (including dose interruptions, total delivered dose and dose modifications) and reasons off treatment.

5. Sample Size and Power

The primary objective of this study is to assess the additional effect of durvalumab and tremelimumab to best supportive care by comparing overall survival (OS) between Durva+Treme and BSC arms among all randomized patients. It was calculated that with a 2-sided alpha of 10%, a total of 180 patients with 150 events (deaths) would be required to provide 80% power to detect a 2.4 month difference in median survival (a hazard ratio of 0.65) between the two treatment arms assuming a median survival of 4.5 months for the BSC alone arm. The final analysis will be conducted after at least 150 events have been recorded. It is estimated that 180 patients accrued over 18 months and followed for 6 months will be required to reach the necessary number of events.

6. Data Set Descriptions

Three types of analysis samples will be used:

All Randomized Patients:

All patients who have been randomized in the study with the treatment arm being as randomized.

Response-Evaluable Patients:

All patients who have received at least one cycle of therapy and have their disease re-evaluated will be considered evaluable for response (exceptions will be those who exhibit objective disease progression prior to the end of cycle 1 who will also be considered evaluable).

All Treated Patients:

All patients on Durva+Treme who received at least one dose of durvalumab and tremelimumab and on BSC who had at least one Best Supportive Care Report.

Patients randomized to BSC who have received at least one dose of durvalumab and tremelimumab on study (from Cancer Treatment Section of Best Supportive Care Report) will be grouped with patients randomized to Durva+Treme in analyses of safety.

7. Statistical Analysis

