7.1 General Methods

All comparisons between treatment arms will be carried out using a two-sided test at an alpha level of 10% unless otherwise specified.

When appropriate, discrete variables are summarized with the number and proportion of subjects falling into each category, and compared using Fisher's exact test. Continuous and ordinal categorical variables are summarized using the mean, median, standard error, minimum and maximum values and when appropriate, compared using the Wilcoxon test. All confidence intervals are computed based on normal approximations except those for rates, which will be computed based on the exact method.

Time to event variables are summarized using Kaplan-Meier plots. Primary comparisons of the treatment groups are made using the stratified log-rank test. Primary estimates of the treatment differences are obtained with the hazard ratios and 90% confidence intervals from stratified Cox regression models using treatment arm as the single factor.

Percentages given in the summary tables will be rounded and may therefore not always add up to exactly 100%. Listings, tabulations, and statistical analyses will be carried out using the SAS (Statistical Analysis System, SAS Institute, North Carolina, USA) software.

Unless otherwise specified, date of randomization and stratification factors will be taken from the Centralized Randomization File.

Baseline evaluations will be those collected on Eligibility Checklist and Baseline Report and closest to, but no later than, the first day of study medication for treated subjects and closest to, but no later than, the date of randomization, for subjects who were randomized but who never received treatment.

Laboratory results, adverse events, and other symptoms are coded and graded using the Common Terminology Criteria for Adverse Events (CTCAE v4.0).

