Treatment arm DURVA+TREME: BSC	**.* (**.*; **.*)	0.***	**.* (**.*; **.*)	0.***
Gender Male: Female	NC ⁽³⁾	0.***	**.* (**.*; **.*)	0.***
Age <65: ≥65	NC	0.***	**.* (**.*; **.*)	0.***
Number of organ sites ≤2: >2	NC	0.***	**.* (**.*; **.*)	0.***
Number of previous chemo drug classes ≤2: >2	NC	0.***	**.* (**.*; **.*)	0.***
Presence of liver metastases No: Yes	NC	0.***	**.* (**.*; **.*)	0.***

(1) Stratified

(2) Stratified Logistic regression, all factors included

(3) NC = not computed

(4) Odds ratio of first category over second category

Table 40: Response According to Pretreatment Characteristics

Data set: All Randomized Patients		
	Number of Responses/Number of Patients (%)	
	DURVA+TREME N=***	BSC N=***
Gender		
Male	**/** (**)	**/** (**)
Female	**/** (**)	**/** (**)
Age		
< 65 years	**/** (**)	**/** (**)
≥ 65 years	**/** (**)	**/** (**)
Race		
White	**/** (**)	**/** (**)
Black	**/** (**)	**/** (**)
Other	**/** (**)	**/** (**)
Baseline performance status		
ECOG 0-1	**/** (**)	**/** (**)
ECOG 2	**/** (**)	**/** (**)
Site of Tumour		
Right colon	**/** (**)	**/** (**)
Transverse colon	**/** (**)	**/** (**)
Left colon	**/** (**)	**/** (**)
Rectum	**/** (**)	**/** (**)
KRAS status		
Wildtype	**/** (**)	**/** (**)
Mutated	**/** (**)	**/** (**)
NRAS status		
Wildtype	**/** (**)	**/** (**)
Mutated	**/** (**)	**/** (**)
BRAF status		
Wildtype	**/** (**)	**/** (**)
Mutated	**/** (**)	**/** (**)
MSI status		
MSI-H	**/** (**)	**/** (**)
MSI-L	**/** (**)	**/** (**)
MSS	**/** (**)	**/** (**)

Table 41: Duration of Response

Data set: All Randomized Patients with CR or PR			
	DURVA+TREME N=***	BSC N=***	P-value ⁽¹⁾
Median Duration of Response (months) (90% CI)	*** (**_**)	*** (**_**)	.**

(1) Stratified

Table 42: Adverse Events on Durvalumab and Tremelimumab Treatment

Data set: All Treated Patients on DURVA+TREME Arm							
	Number of patients (%) N=***						
	Worst grade						Any grade
	NR	1	2	3	4	5	
Patients with any AE	** (**)	** (**)	** (**)	** (**)	** (**)	** (**)	** (**)
Patients with AE within category							
Category 1 ⁽¹⁾	** (**)	** (**)	** (**)	** (**)	** (**)	** (**)	** (**)
Event 1	** (**)	** (**)	** (**)	** (**)	** (**)	** (**)	** (**)
Event 2	** (**)	** (**)	** (**)	** (**)	** (**)	** (**)	** (**)
Event 3	** (**)	** (**)	** (**)	** (**)	** (**)	** (**)	** (**)
...							

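### If no BSC patient responds, both planned treatment odds ratios for ORR are infinite, leaving the comparison with a p-value but no usable effect size.

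*SAP*

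**What the plan says.** ORR is a secondary endpoint in both documents. Protocol 13.2 defines it as a proportion, bases the primary estimate on all randomized patients and compares the arms with a stratified CMH test. SAP 7.6.5 keeps that test as the primary response analysis. It then says that "a stratified logistic regression model adjusted for covariates will be applied", promises odds ratios with 90% CIs for every stratified logistic model, and gives the method: "Stratified logistic regression odds ratios will be estimated using PROC PHREG in SAS". The device is a dummy time variable with the DISCRETE option for ties, which is conditional logistic regression.

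Table 39 has two treatment odds ratios, each with a 90% CI: a stratified univariate one beside the CMH p-value, and one from the covariate-adjusted model. SAP 7.6.1 lists four prognostic factors. The Table 39 shell has a fifth, "Number of previous chemo drug classes".

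SAP 7.1 computes all confidence intervals by normal approximation, except those for rates, which are exact. An odds ratio is not a rate, so its interval is of Wald type. Neither document says what to do when an arm has no responders. On size, SAP 2.1 says "A total of 180 patients would be enrolled (120 on Durva+Treme and 60 on BSC").

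**The concern.** BSC is defined in Protocol 7.1.1 as palliative measures, and eligibility criterion 4.1.8 requires it to be the only remaining standard option. An arm of 60 such patients with no objective response is therefore foreseeable. In that case a treatment odds ratio has a zero in its denominator and a Wald interval has no finite estimate to be centred on. The software may still print a number, set by its convergence rule rather than by the data, and a reader could take it for a result. The team would then have to choose a rescue method after seeing who responded. At stake is the size of effect for a declared secondary endpoint. Overall survival, the primary endpoint, is not affected.

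**Working it through.** **The plan's own design figure.** The only one concerns survival: "a total of 180 patients with 150 events (deaths) would be required to provide 80% power" (SAP section 5), for a "35% reduction in the continuous risk of death (HR 0.65") in Protocol 13.3. With two-sided alpha 10% and 2:1 allocation, the Schoenfeld formula gives (1.645 + 0.842)² / [(1/3)(2/3)(ln 0.65)²] = 6.183 / 0.04124 = 149.9, so 150 is reproduced. It says nothing about ORR. No response rate or ORR power is stated for either arm.

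**Inputs.** 120 and 60 patients (SAP 2.1). Ten strata: two ECOG levels by five tumour sites (SAP 2.2). The BSC response rate p is not given and is assumed to lie between 0% and 2%.

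**Chance of no BSC responder, (1 − p)^60.**

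| Assumed p | P(0 of 60) |
|---|---|
| 0% | 100% |
| 0.5% | 74% |
| 1% | 55% |
| 2% | 30% |
| 3% (beyond the range) | 16% |

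The value exceeds 50% when p is below 1 − 0.5^(1/60) = 1.15%. A simulation over ten strata (2,000 runs per scenario, assumed stratum shares, Arm 2 rates of 2% to 10%) gave much the same chance of an inestimable treatment odds ratio: 100%, 73–77%, 54–58% and 29–39% at p = 0%, 0.5%, 1% and 2%.

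**What happens to the odds ratio.** Take an illustrative 6/120 against 0/60, with Arm 2:BSC stratum sizes 24:12, 22:11, 8:4, 30:15, 16:8 and 20:10 and Arm 2 responders 2, 1, 0, 2, 1 and 0.

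- At a treatment coefficient of 0 the conditional likelihood is (276/630)(22/33)(435/990)(16/24) = 0.0856, so its log is −2.46.
- The log-likelihood then rises without turning: −0.40 at coefficient 2, −0.021 at 5, −0.001 at 8, tending to 0. There is no finite maximum.
- The Mantel-Haenszel odds ratio has denominator 0, so the univariate entry in Table 39 is infinite by that route too.
- The CMH statistic is still computable: 3.05, p = 0.08.

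**A covariate-adjusted fit.** In one simulated dataset with 8 against 0 responders, ten strata and four covariates (fitted outside SAS), the treatment coefficient moved from 2.2 (SE 1.9) to 10.6 (SE 110) as more iterations were allowed. The Wald 90% interval at the end is 10.6 ± 1.645 × 110, about −170 to 192 on the log scale. The four covariate coefficients settled.

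**What other methods give for 6/120 against 0/60.**

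- Odds ratio: a one-sided 95% exact conditional lower bound of 0.78 and a 90% profile-likelihood lower bound of 2.0, with no finite upper limit.
- Risk difference: 5.0 points. The Wilson 90% limits are 2.6% to 9.4% for 6/120 and 0% to 4.3% for 0/60. The unstratified Newcombe limits are 5.0 − √[(5.0 − 2.61)² + 4.31²] = 0.1 and 5.0 + (9.4 − 5.0) = 9.4 points.
- BSC rate: exact upper limit 1 − 0.05^(1/60) = 4.9%.

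The risk difference and the rate have finite limits on both sides.

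**The case against.** The strongest reply is that little is lost. CMH is the primary analysis of response. The adjusted logistic model is introduced as an addition, to check the influence of prognostic factors, and the Protocol plans no logistic model for ORR. Table 38 reports CR and PR counts and percentages per arm out of all randomized patients, and SAP 7.1 already makes intervals for rates exact. A reader might infer that ORR would be left with no estimate at all. The documents do not support that: both arm rates are available and their difference is a subtraction. What stands is that no interval for the difference is planned, and that the Table 38 shell has neither a combined CR+PR row nor a CI.

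A reader might also blame the covariate adjustment. That is not the cause, because the univariate stratified odds ratio fails in the same way. Few responders across ten strata make the adjusted model fragile besides: at an assumed Arm 2 rate of 3–5%, 3.6 to 6 Arm 2 responders are expected. But separation comes from the empty arm. It would arise equally with the 12 responders implied by the roughly 10% anti-CTLA-4 class rate in Protocol 3.2.5, a figure not specific to this population.

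Nor is everything inestimable. Covariate effects can converge, and the treatment odds ratio has a lower bound. It is the planned Wald interval that fails.

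Finally, the likelihood of an empty BSC arm rests on an assumption. SAP 7.6.3 records that some patients received other anti-cancer therapy before progression, so a BSC response is possible. This is fair, and it is why a range is shown.

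**Conclusion.** The point holds. Followed as written, the SAP yields an infinite treatment odds ratio and an uninformative 90% CI, in both columns of Table 39, whenever BSC has no responder and Arm 2 has at least one. The risk is 30% or more for any true BSC rate up to 2%, and above one half below about 1.15%. These rates are assumptions; the documents do not establish that BSC will have no responders. The CMH p-value stands whenever anyone responds. The loss is confined to the between-arm effect size and its interval for a secondary endpoint. The failure can be foreseen and the remedy is cheap, so the SAP should be changed before analysis.

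**What to change.** In SAP 7.6.5 and Table 39:

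1. Keep the stratified CMH test as the primary test.
2. Make the Mantel-Haenszel stratified risk difference, with a score-type 90% CI, the primary between-arm estimate, and name the interval method.
3. Show the combined CR+PR rate per arm with its exact 90% CI, which applies the existing SAP 7.1 convention.
4. Keep both odds ratios as supportive. When an arm has no responders, replace the Wald interval by an exact conditional or profile-likelihood one-sided interval. Say in advance which.
5. Reconcile the Table 39 covariates with the four listed in SAP 7.6.1.

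Fitting the adjusted model only above a minimum of, say, five responders per arm is not advised. The chance of five or more among 60 BSC patients is 0.03% at a 1% rate and 0.7% at 2%, so the rule would in effect delete that analysis.

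The cost is SAP wording and one more table row, with no new data. The small downside is that the adjusted odds ratio may be only a bound when responders are few.
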